11.6.3.4. Sensitivity Analysis for Potential Data Integrity Issues

In case where there are data integrity issues, that could potentially impact the primary analysis outcome of the trial, we will perform a sensitivity analysis by excluding certain sites from the primary analysis.

One site in Poland (site ID = **PPD** has been stopped due to significant GCP concerns. A sensitivity analysis, with data from this site excluded, will be performed. For this, the planned primary analysis will be generated without data from this site. The results will be used to assess potential impact of data from this particular site on the primary analysis results.

11.7. Appendix 7: Values of Potential Clinical Importance

11.7.1. Laboratory

Hematology			
Laboratory Test	Units	Change from Baseline of Potential Clinical Concern	Potential Clinical Concern Value
Basophils	Gl/L	None	None
Eosinophils	Gl/L	None	None
Hematocrit	1	>0.1 decrease	>0.05 below LLN >0.04 above ULN
Hemoglobin	g/L	>25 g/L decrease	>20 g/L below LLN >10 g/L above ULN
Lymphocytes	Gl/L	None	<0.5 x LLN
Monocytes	Gl/L	None	None
Neutrophils	Gl/L	None	<1 Gl/L
Neutrophil Bands	Gl/L	None	None
Platelets	Gl/L	None	<80 Gl/L >500 Gl/L
Red Blood Cell Count	Tl/L	None	None
Segmented Neutrophils	Gl/L	None	<0.5 x LLN
White Blood Cell Count	Gl/L	None	>1 Gl/L below LLN >5 Gl/L above ULN

Chemistry			
Laboratory Test	Units	Change from Baseline of Potential Clinical Concern	Potential Clinical Concern Value
Albumin	g/L	None	>5 g/L above ULN or below LLN
Alkaline Phosphatase	U/L	None	>3 x ULN
ALT	U/L	None	>3 x ULN
AST	U/L	None	>3 x ULN
Bicarbonate (Carbon Dioxide Content)	mmol/L	None	<16 mmol/L > 40 mmol/L
Blood Urea Nitrogen	mmol/L	None	>2 x ULN
Calcitonin	pmol/L	None	>100
Calcium	mmol/L	None	<1.8 mmol/L

Chemistry			
Laboratory Test	Units	Change from Baseline of Potential Clinical Concern	Potential Clinical Concern Value
			>3.0 mmol/L
Chloride	mmol/L	None	None
Creatinine	umol/L	None	>159 umol/L
Direct Bilirubin	umol/L	None	>1.35 x ULN
Gamma Glutamyl Transferase	U/L	None	>3 x ULN
Glucose (fasting)	mmol/L	None	<3 mmol/L >22 mmol/L
Magnesium	mmol/L	None	<0.411 mmol/L >1.644 mmol/L
Phosphorus	mmol/L	None	>0.323 mmol/L above ULN or below LLN
Potassium	mmol/L	None	>0.5 mmol/L below LLN >1.0 mmol/L above ULN
Sodium	mmol/L	None	>5 mmol/L above ULN or below LLN
Total Bilirubin	umol/L	None	>1.5 x ULN
Total Protein	g/L	None	>15 g/L above ULN or below LLN
Uric acid	umol/L	None	>654 umol/L
Free Fatty Acids	mmol/L	None	None
HDL Cholesterol	mmol/L	None	None
LDL Cholesterol	mmol/L	None	None
Triglycerides	mmol/L	None	> 9.04 mmol/L
Total Cholesterol	mmol/L	None	None

Urinalysis	
Laboratory Test	Potential Clinical Concern Value
Urinalysis Albumin/Creatinine Ratio	>29 mg/g (>3.4 mg/mmol in SI units)

Liver Function Tests	
Laboratory Test	Potential Clinical Concern Value
ALT	$\geq 2 \times \text{ULN}$ $\geq 3 \times \text{ULN}$ $\geq 5 \times \text{ULN}$ $\geq 8 \times \text{ULN}$ $\geq 10 \times \text{ULN}$ $\geq 3 \times \text{ULN}$ and Total Bilirubin $\geq 2 \times \text{ULN}$
AST	$\geq 2 \times \text{ULN}$ $\geq 3 \times \text{ULN}$ $\geq 5 \times \text{ULN}$ $\geq 8 \times \text{ULN}$ $\geq 10 \times \text{ULN}$ $\geq 3 \times \text{ULN}$ and Total Bilirubin $\geq 2 \times \text{ULN}$
Total Bilirubin	$\geq 1.5 \times \text{ULN}$ $\geq 2 \times \text{ULN}$ $\geq 3 \times \text{ULN}$ $\geq 5 \times \text{ULN}$ $\geq 8 \times \text{ULN}$ $\geq 10 \times \text{ULN}$

11.7.2. Vital Signs

Parameter	Units	Change from Baseline of Potential Clinical Concern	Potential Clinical Concern Value
Systolic BP	mmHg	Decrease $>30 \text{ mmHg}$ Increase $>30 \text{ mmHg}$	$<100 \text{ mmHg}$ $>170 \text{ mmHg}$
Diastolic BP	mmHg	Decrease $>30 \text{ mmHg}$ Increase $>30 \text{ mmHg}$	$<50 \text{ mmHg}$ $>110 \text{ mmHg}$
Heart rate	bpm	Decrease $>30 \text{ bpm}$ Increase $>30 \text{ bpm}$	$<50 \text{ bpm}$ $>120 \text{ bpm}$

11.7.3. ECG

Parameter	Units	Change from Baseline of Potential Clinical Concern	Potential Clinical Concern Value
Heart Rate	bpm	None	Supine: < 50 or > 120
QRS interval	msec	Increase of > 25% when baseline QRS >100 msec Increase of > 50% when baseline QRS ≤100 msec	>200 msec
QTcF	msec	≥ 60 msec	≥500 msec
PR Interval	msec	Increase of > 25% when baseline PR >200 msec Increase of > 50% when baseline PR ≤200 msec	>300 msec

11.8. Appendix 8: Multicenter Studies and Definition of Geographic Region for Statistical Analyses

Clinical sites will be clustered by geographic region since the number of subjects per clinical site is expected to be rather small. Geographic regions will be defined based on geographic proximity, similarity of medical practice in diabetes, and number of subjects per region. Subjects per region will be constrained such that the region with the largest sample size is no more than 3 times that of the region with the smallest sample size. The clustering will be finalized after clinical site selection and randomization are complete.

Final classification of Geographic region for clinical sites:

- Region 1: United States and Canada;
- Region 2: Mexico;
- Region 3: Brazil;
- Region 4: Poland and Hungary;
- Region 5: Germany, France, Spain, Italy and United Kingdom;
- Region 6: Philippines, South Africa and Korea.

11.9. Appendix 9: Examination of Covariates, Subgroups & Other Strata

11.9.1. Strata and Covariates

The randomization for this study is stratified by the following baseline characteristics:

- HbA_{1c} at Screening (<8.0% versus $\geq 8.0\%$)
- Age at randomization (<65 years versus ≥ 65 years)
- Current use of metformin (metformin use versus no metformin use)

The primary analysis of HbA_{1c} change from Baseline will use a mixed-effect model with repeated measures (MMRM), which includes HbA_{1c} change from Baseline at all postbaseline visits as dependent variables; treatment, region, age category, current use of metformin, visit week, treatment-by-week interaction, and baseline HbA_{1c}-by-week interaction as fixed effects; baseline HbA_{1c} as a continuous covariate; and subject as a random effect. MMRM will only include non-missing observations therefore imputation will not be performed.

11.9.2. Examination of Subgroups

The primary efficacy endpoint will be analyzed for the following subgroups using a MMRM model described in Section 7.

- Baseline HbA_{1c} (<8.0%, $\geq 8.0\%$)
- Gender (male, female)
- Race (white, non-white)
- Ethnicity (Hispanic, non-Hispanic)
- Age at randomization (<65 years, ≥ 65 years)
- Baseline BMI (<25 kg/m², ≥ 25 to <30 kg/m², ≥ 30 to <35 kg/m², ≥ 35 kg/m²)
- Region (Region 1, Region 2, Region 3, Region4, Region5, Region 6)
- Duration of Type II diabetes (< 8 years, ≥ 8 - ≤ 13 years, > 13 years)
- Current use of metformin (metformin use, no metformin use)
- Baseline FPG tertiles

11.10. Appendix 10: Multiple Comparisons & Multiplicity

A closed testing strategy will be implemented for the multiple inferential tests among the primary and key secondary endpoints to preserve overall family-wise Type I error rate of 0.05. The strategy involves pre-specification of test order [Koch, 1996].

The first test to be conducted is the primary efficacy analysis of HbA_{1c} change from Baseline at Week 26 on treatment comparison of albiglutide versus insulin lispro using non-inferiority testing. The comparison will be evaluated inferentially at the 1-sided 0.025 criterion significance level. If the non-inferiority of albiglutide is established, testing of superiority for the key secondary endpoints and the primary endpoint will proceed sequentially in a step-down manner at a 2-sided significance level of 0.05 in the following order:

- 1) Change from Baseline in body weight at Week 26
- 2) Prescribed total daily insulin dose at Week 26
- 3) Change from baseline in HbA_{1c} at Week 26

If a test for higher order endpoints above does not reach statistical significance, the results of statistical tests for lower order endpoints will not be interpreted.

Note that for one of the key secondary endpoints listed in the protocol, proportion of subjects treated with once-weekly albiglutide that are able to discontinue insulin lispro at Week 4 and do not meet prespecified criteria for severe, persistent hyperglycemia through Week 26, treatment comparison is not applicable as it is only defined for the Albiglutide + Insulin Glargine arm.

This is a treat-to-target study with the primary efficacy endpoint HbA_{1c} as the measurement. By the study design of treat-to-target, change from baseline in HbA_{1c} values in both treatment groups (Albiglutide + Insulin Glargine versus Insulin Lispro + Insulin Glargine), is expected to reach the target, and thus not expected to show a significant difference. Thus, testing of superiority for change from Baseline in HbA_{1c} at Week 26 is considered lowest priority in the hierarchy of the multiple testing procedure.

Testing on other efficacy or exploratory endpoints, if applicable, will be considered exploratory and no multiplicity adjustment will be applied. Any secondary and exploratory endpoints that do not qualify for formal statistical testing will be analyzed and have results presented with confidence intervals and nominal p-values, if applicable.

The order of the testing strategy is shown in the diagram below.

Albiglutide + Insulin Glargine versus Insulin Lispro + Insulin Glargine

Primary Efficacy Endpoint -
HbA1c Change from Baseline at

Key Secondary Efficacy Endpoint
1 - Percentage of subjects with

Key Secondary Efficacy Endpoint
2 - Change from Baseline in body

Key Secondary Efficacy Endpoint
3 - Total daily insulin dose at

Primary Efficacy Endpoint -
HbA1c Change from Baseline at

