2.2. Study Objectives and Endpoints

Objectives	Endpoints
Primary	

 To evaluate the glycemic effectiveness of once-weekly albiglutide as replacement of prandial insulin in subjects with T2DM receiving basal-bolus insulin therapy 	
 Change from Baseline in HbA_{1c} at Week 26
Key Secondary	

 To determine the proportion of subjects treated with once-weekly albiglutide that are able to replace prandial insulin without the need for re-introduction of insulin lispro 	
 Proportion of subjects treated with once-weekly albiglutide that are able to discontinue insulin lispro at Week 4 and do not meet prespecified criteria for severe, persistent hyperglycemia through Week 26

 To demonstrate a significant difference in the frequency of hypoglycemic events between treatment groups 	
 Percentage of subjects with severe or documented symptomatic hypoglycemia through Week 26

 To demonstrate a significant difference in body weight between treatment groups 	
 Change from Baseline in body weight at Week 26 and over time

 To demonstrate a significant 	
 Prescribed total daily insulin dose at Week 26

[figure not shown]
Objectives	Endpoints
reduction in total daily dose of insulin between treatment groups	
Supportive Secondary	

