2.4. Statistical Hypotheses

The primary hypothesis to be tested is that albiglutide plus insulin glargine (with or without metformin) will provide glycemic control (as measured by HbA_{1c} change from Baseline) noninferior to insulin lispro plus insulin glargine (with or without metformin) after 26 weeks of treatment in subjects with T2DM inadequately controlled on their current regimen of basal-bolus insulin therapy. If the null hypothesis of albiglutide inferiority is rejected, a test of superiority will be applied.

- The null hypothesis is that the difference in the mean change from Baseline to Week 26 in HbA_{1c} between albiglutide and insulin lispro is greater than the non-inferiority margin of 0.3%.
- The alternative hypothesis is that the difference in the mean change from Baseline to Week 26 in HbA_{1c} between albiglutide and insulin lispro is less than or equal to the non-inferiority margin of 0.3%.

The null hypothesis will be tested based on the upper bound of 1-sided 97.5% confidence interval (equivalently, the upper bound of a 2-sided 95% confidence interval) of the least squares mean of the treatment difference estimated from a MMRM model. The MMRM model will include HbA_{1c} change from Baseline as the dependent variable, treatment, region, age category, current use of metformin, visit week, treatment-by-week interaction, and baseline HbA_{1c}-by-week interaction as the fixed effects, and baseline HbA_{1c} as a continuous covariate. Subject will be included in the model as a random effect. If the upper bound of 1-sided 97.5% confidence interval is less than or equal to 0.3%, non-inferiority will be concluded. If non-inferiority is established, a superiority test will be performed and the upper bound of 1-sided 97.5% confidence interval will be compared to 0. If it is less than 0, superiority will be claimed. This superiority test with respect to HbA_{1c} will be performed after testing the key secondary hypotheses.

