5.1. Multiple Comparisons and Multiplicity

A multiple comparisons adjustment strategy will be implemented for the multiple inferential tests among the primary and key secondary endpoints to preserve the family-wise Type I error rate of 0.05. Testing on other efficacy endpoints will be considered

exploratory and no multiplicity adjustment will be applied. Details are provided in [Appendix 10: Multiple Comparisons and Multiplicity](#).

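### SAP Appendix 10 gives two conflicting step-down orders: the list starts with body weight, the diagram puts a percentage endpoint (inferred to be hypoglycemia) ahead of it

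*SAP*

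**What the plan says.** SAP Appendix 10 (section 11.10) sets a fixed-sequence procedure to hold the family-wise error at 0.05. HbA1c non-inferiority is tested first, at one-sided 0.025. Superiority tests then follow at two-sided 0.05, and a failed step stops interpretation of everything below it.

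The order of the superiority tests is given twice.

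- **Numbered list:** "1) Change from Baseline in body weight at Week 26", then prescribed total daily insulin dose, then HbA1c. Hypoglycemia is absent.
- **Diagram:** introduced with "The order of the testing strategy is shown in the diagram below". Its boxes after non-inferiority are key secondary "1 - Percentage of subjects with" (label cut off), key secondary "2 - Change from Baseline in body" (also cut off), key secondary 3 for total daily insulin dose, then HbA1c.

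Other places that bear on the point:

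- SAP 5.1: "A multiple comparisons adjustment strategy will be implemented for the multiple inferential tests among the primary and key secondary endpoints", to preserve the 0.05.
- SAP 2.4: the HbA1c superiority test "will be performed after testing the key secondary hypotheses".
- SAP 2.2 lists as a key secondary objective: "To demonstrate a significant difference in the frequency of hypoglycemic events between treatment groups".
- SAP 8.1.2.2 plans a stratified Cochran-Mantel-Haenszel (CMH) test for that endpoint.
- Appendix 10 explains why one key secondary endpoint, the albiglutide-only proportion, is not compared between arms. It gives no such explanation for hypoglycemia.
- Appendix 10 also says that secondary and exploratory "endpoints that do not qualify for formal statistical testing will be analyzed and have results presented with confidence intervals and nominal p-values".

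**The concern.** A fixed-sequence procedure rests on one order, set in advance. Here two are written, each introduced as the order. They differ in length (three superiority steps against four) and in where weight stands (first against second).

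At stake is which claims count as confirmatory. The hypoglycemia comparison is either the first test after non-inferiority or outside the controlled family altogether. In the first case it can also bar the weight and insulin-dose claims; in the second it cannot. The trial is open-label (Protocol 5.3), so blinding gives no protection against a late choice between the two.

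**Working it through.** **1. Is the conflict an artefact of the text extraction?** No. The list is numbered 1 to 3 without a gap. In the diagram only the ends of the labels are lost, and the numbers survive. Weight is 1 in one version and 2 in the other.

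**2. What is box 1?** Of the key secondary endpoints in SAP 2.2, only severe or documented symptomatic hypoglycemia is worded as a percentage of subjects. The other binary endpoint is worded as a proportion and is expressly excluded from comparison. Hypoglycemia is therefore a strong inference, to be confirmed against the figure in the PDF. The numbering conflict does not depend on it; the consequences below do.

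**3. Does anything settle precedence?** Protocol 8.3.3.2 defers the details to the analysis plan. SAP 7.1.1.1 points back to Appendix 10. SAP 2.4 and 5.1 speak of the key secondary endpoints without ranking them. The change table in SAP 2.1 does not mention dropping hypoglycemia.

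**4. Consequences once non-inferiority is met**

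| Hypoglycemia result | Under the diagram | Under the list |
|---|---|---|
| p < 0.05 | Confirmatory; weight tested next | Nominal only; weight tested regardless |
| p ≥ 0.05 | Weight, dose and HbA1c superiority not interpreted | Weight, dose and HbA1c still tested in sequence |

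**5. The plan's own figures (SAP Appendix 12).** With margin 0.3, SD 1.2, true difference 0 and 337 completers per arm:

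- SE = 1.2 × √(2/337) = 0.0924.
- Power = Φ(0.3/0.0924 − 1.96) = 0.901 (0.900 with the t distribution), as stated.
- Randomized per arm = 337/0.85 = 396.5, rounded up to 397; 794 in total.

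These reproduce and are not affected by the conflict.

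**6. Chance that the diagram blocks what the list allows.** The documents give no hypoglycemia rate, so control rates *p*c are assumed. The Protocol Summary reports about 1.5- to 2-fold less symptomatic hypoglycemia in earlier studies. I apply that ratio *r* to subject proportions, which is a further assumption. With *p*t = *p*c/*r*, p̄ the mean of the two and n = 397 per arm, unstratified as an approximation to the CMH test:

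Power = Φ{ [ (*p*c − *p*t) − 1.96 √(2p̄(1−p̄)/n) ] / √[ (*p*c(1−*p*c) + *p*t(1−*p*t))/n ] }

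Example, *p*c = 0.20 and *r* = 1.5: Φ[(0.0667 − 1.96 × 0.02645)/0.02635] = Φ(0.56) = 0.713.

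| Control rate | Power, 1.5-fold | Blocked | Power, 2-fold | Blocked |
|---|---|---|---|---|
| 20% | 71.3% | 28.7% | 97.8% | 2.2% |
| 30% | 90.4% | 9.6% | 99.9% | 0.1% |
| 40% | 98.0% | 2.0% | >99.9% | <0.1% |
| 50% | 99.8% | 0.2% | >99.9% | <0.1% |

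These are conditional on passing non-inferiority. Multiplying by its planned 90% power, and treating the tests as independent, 28.7% becomes about 26% and 9.6% about 9%.

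**7. Family-wise error, hypoglycemia and weight both truly null, non-inferiority passed**

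- List alone 5.0%; diagram alone 5.0% (simulation gives 0.050 for each).
- Either claimed at 0.05, independent tests: 1 − 0.95² = 0.0975.
- Correlated test statistics, 1 − P(|Z₁| < 1.96, |Z₂| < 1.96): 0.0907 at correlation 0.5 and 0.0781 at 0.8.
- Upper bound: 0.05 + 0.05 = 0.10.

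**The case against.** The strongest reply is that the list is operative and the diagram was simply not updated. The list uses the term prescribed for insulin dose, as SAP 2.1 and 2.2 do, while the diagram keeps the protocol's wording. The stopping rule directly follows the list and refers to the endpoints above it. Weight, dose and HbA1c run in the same sequence in both, so the dispute is about one extra endpoint. The sentence on nominal p-values could cover hypoglycemia, which would make the list workable as it stands.

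Much of this is fair. The wording leans slightly towards the list, and the defect is as much about membership as about order. But it remains an inference. The appendix gives the diagram the same authority as the list, explains the omission of a different endpoint and not this one, and leaves hypoglycemia with an objective of demonstrating a significant difference. Treating it as nominal also sits badly with SAP 5.1, which places the key secondary endpoints in the controlled family.

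It is also true that 9.75% is not the error of either written procedure, that the blocking risk is small except at 1.5-fold with low control rates, and that the earlier ratio may describe events rather than subjects. These points limit the size of the blocking risk and of the error inflation. They do not touch the other consequence: the higher the power for hypoglycemia, the more likely it is that its significant result is confirmatory under one version and nominal under the other.

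**Conclusion.** The concern holds. Appendix 10 contradicts itself on which endpoint is tested first after non-inferiority and on whether hypoglycemia is in the confirmatory family, and nothing in either document resolves it. The set of confirmatory claims is therefore undefined as written.

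The 0.05 is preserved under either version if that version is fixed in advance. It is exceeded (9.75% if independent, 10% at most) only if hypoglycemia is claimed at 0.05 alongside the list, or if the order is picked after the data are seen. Conditional on non-inferiority, the chance that the versions disagree on whether weight and dose may be interpreted runs from about 29% (1.5-fold, 20% control rate) to about 2% or less (2-fold, any control rate from 20%). This rests on assumed control rates, on the reported ratio applying to subject proportions, and on box 1 being hypoglycemia. The primary test and the sample size are unaffected.

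**What to change.** Before database lock, confirm the label of box 1 and make list and diagram identical by one of two routes.

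(a) Add the percentage of subjects with severe or documented symptomatic hypoglycemia through Week 26 (CMH, two-sided 0.05) to the list at the diagram's rank, and renumber weight, insulin dose and HbA1c superiority as 2 to 4.

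(b) Remove that box from the diagram and state that the hypoglycemia p-value is nominal. Amend SAP 5.1 and the family definition in Appendix 10 to place this key secondary endpoint outside the confirmatory family, and record the decision in SAP 2.1. A matching clarification in SAP 2.4 is useful but optional, since its sentence stays true for weight and dose.

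The edit is to SAP wording only. Under (a) the weight and insulin-dose claims depend on hypoglycemia reaching significance. Under (b) the sponsor gives up a confirmatory hypoglycemia claim.

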11.11. Appendix 11: Model Checking and Diagnostics for Statistical Analyses

11.11.1. Model Checking and Diagnostics for Statistical Analyses

1. Example SAS code for the primary efficacy analysis of the primary endpoint (Model 1)

```
ODS OUTPUT LSMeans= OUTLIBNAME.LSMeans SLICES= OUTLIBNAME.Diffs;
PROC MIXED DATA= INDATA;
  CLASS USUBJID TRT01PN REGION METFORMIN AGEGR1 AVISITN;
  MODEL CHG = BASE TRT01PN REGION METFORMIN AGEGR1 AVISITN
    TRT01PN*AVISITN BASE*AVISITN /DDFM =KR ;
  REPEATED AVISITN/SUB=USUBJID TYPE=UN;
  LSMEANS TRT01PN*AVISITN/SLICE=AVISITN CL DIFF;
  ESTIMATE 'Treatment difference at Week 26'
    TRT01PN 1 -1
    TRT01PN*AVISITN 0 0 0 0 1
                  0 0 0 0 -1 /CL ;
RUN;
```

2. Example SAS code for the supportive analysis – interaction terms- of the primary endpoint

For HbA1c (Baseline HbA1c category: HBGR1):

```
ODS OUTPUT LSMeans= OUTLIBNAME.LSMeans SLICES= OUTLIBNAME.Diffs;
PROC MIXED DATA= INDATA;
  CLASS USUBJID TRT01PN REGION METFORMIN AGEGR1 AVISITN HBGR1;
  MODEL CHG = HBGR1 TRT01PN REGION METFORMIN AGEGR1 AVISITN
    TRT01PN*AVISITN HBGR1*AVISITN TRT01PN*HBGR1
    TRT01PN*HBGR1*AVISITN /DDFM =KR ;
  REPEATED AVISITN/SUB=USUBJID TYPE=UN;
  LSMEANS TRT01PN*HBGR1*AVISITN/SLICE=AVISITN CL DIFF;

  ESTIMATE 'Treatment difference at Week 26 for Baseline HbA1c
  Category < 8.0%'
    TRT01PN 1 -1
    TRT01PN*AVISITN 0 0 0 0 1 0 0 0 0 -1
    TRT01PN*HBGR1*AVISITN 0 0 0 0 0 0 0 0 1 0
                          0 0 0 0 0 0 0 0 -1 0 /CL ;
RUN;
```

(or use the following statement to replace the 'LSMEANS' AND 'ESTIMATE' statements above:
SLICE HBR1*TRT01PN*AVISITN/SLICEBY(AVISITN='26') DIFF; and ODS table SLICETESTS to obtain p-value for the interaction at Week 26 (AVISITN=26).

For Age category, Metformin use or Region:

```
ODS OUTPUT LSMeans= OUTLIBNAME.LSMeans SLICES= OUTLIBNAME.Diffs;
PROC MIXED DATA= INDATA;
  CLASS USUBJID TRT01PN REGION METFORMIN AGEGR1 AVISITN;
  MODEL CHG = BASE TRT01PN REGION METFORMIN AGEGR1 AVISITN
    TRT01PN*AVISITN BASE*AVISITN TRT01PN*AGEGR1
    AVISITN*AGEGR1 TRT01PN*AGEGR1*AVISITN /DDFM =KR ;
  REPEATED AVISITN/SUB=USUBJID TYPE=UN;
  LSMEANS TRT01PN*AGEGR1*AVISITN /SLICE=AVISITN CL DIFF;

  ESTIMATE 'Treatment difference at Week 26 for Age category < 65'
    TRT01PN 1 -1
    TRT01PN*AVISITN      0 0 0 0 1 0 0 0 0 -1
    TRT01PN*AGEGR1*AVISITN 0 0 0 0 1 0 0 0 0 0
    0 0 0 0 -1 0 0 0 0 0 /CL ;
```

RUN;

Note: The contrasts may need to be adjusted for a different factor.

(or use the following statement to replace the 'LSMEANS' AND 'ESTIMATE' statements above:
SLICE HBR1*TRT01PN*AVISITN/SLICEBY(AVISITN='26') DIFF; and ODS table SLICETESTS to obtain p-value for the interaction at Week 26 (AVISITN=26).

3. Example SAS code for the by-subgroup analysis of the primary endpoint

Take by-FPG Tertiles as an example

```
ODS OUTPUT LSMeans= OUTLIBNAME.LSMeans SLICES= OUTLIBNAME.Diffs;
PROC MIXED DATA= INDATA;
  CLASS USUBJID TRT01PN REGION METFORMIN AGEGR1 FPG_TTL AVISITN;
  MODEL CHG= BASE TRT01PN REGION METFORMIN AGEGR1 FPG_TTL
    AVISITN TRT01PN*AVISITN BASE*AVISITN
    TRT01PN*FPG_TTL FPG_TTL*AVISITN
    TRT01PN*FPG_TTL*AVISITN /DDFM =KR ;
  REPEATED AVISITN/SUB=USUBJID TYPE=UN;
  LSMEANS TRT01PN*FPG_TTL*AVISITN/SLICE=AVISITN CL DIFF;
  ESTIMATE 'Treatment difference at Week 26 for 1st Baseline FPG
  Tertile'
    TRT01PN -1 1
    TRT01PN*AVISITN      0 0 0 0 1 0 0 0 0 -1
    TRT01PN*FPG_TTL*AVISITN 0 0 0 0 1 0 0 0 0 0
    0 0 0 0 0 0 0 0 0 -1
    0 0 0 0 0 0 0 0 0 0 /CL ;
```

RUN;

For Age category

Use the same SAS code for the supportive analysis on interaction terms.

For Baseline HbA1c category

```
ODS OUTPUT LSMeans= OUTLIBNAME.LSMeans SLICES= OUTLIBNAME.Diffs;
PROC MIXED DATA= INDATA;
  CLASS USUBJID TRT01PN REGION METFORMIN AGEGR1 HBGR1 AVISITN;
  MODEL CHG= HBGR1 TRT01PN REGION METFORMIN AGEGR1 AVISITN
    TRT01PN*AVISITN HBGR1*AVISITN
    TRT01PN*HBGR1*AVISITN/DDFM =KR ;
  REPEATED AVISITN/SUB=USUBJID TYPE=UN;
  LSMEANS TRT01PN*AVISITN/SLICE=AVISITN CL DIFF;
  ESTIMATE 'Treatment difference at Week 26 for Baseline HbA1c
<8.0%'
    TRT01PN -1 1
    TRT01PN*AVISITN      0 0 0 0 1 0 0 0 0 -1
    TRT01PN*HBGR1*AVISITN 0 0 0 0 1 0 0 0 0 0
    0 0 0 0 -1 0 0 0 0 0 /CL ;
RUN;
```

4. Example SAS code for key secondary efficacy endpoints Weight, Insulin dose etc (Model 2)

```
ODS OUTPUT LSMeans= OUTLIBNAME.LSMeans SLICES= OUTLIBNAME.Diffs;
PROC MIXED DATA= INDATA;
  CLASS USUBJID TRT01PN REGION METFORMIN AGEGR1 AVISITN HBGR1;
  MODEL CHG= BASE TRT01PN HBGR1 REGION METFORMIN AGEGR1 AVISITN
    TRT01PN*AVISITN BASE*AVISITN /DDFM =KR ;
  REPEATED AVISITN/SUB=USUBJID TYPE=UN;
  LSMEANS TRT01PN*AVISITN/SLICE=AVISITN CL DIFF;
  ESTIMATE 'Treatment difference at Week 26'
    TRT01PN -1 1
    TRT01PN*AVISITN 0 0 0 0 -1
    0 0 0 0 1 /CL ;
RUN;
```

Note: The contrasts may need to be adjusted for an endpoint that has a different visit scheme from that of HbA1c.

5. Example SAS code for analysis on FPG change from baseline by baseline FPG tertiles

```
ODS OUTPUT LSMeans= OUTLIBNAME.LSMeans SLICES= OUTLIBNAME.Diffs;
PROC MIXED DATA= INDATA;
  CLASS USUBJID TRT01PN REGION METFORMIN AGEGR1 HBGR1 FPG_TTL
    AVISITN;
  MODEL CHG= FPG_TTL HBGR1 TRT01PN REGION METFORMIN AGEGR1
    AVISITN TRT01PN*AVISITN TRT01PN*FPG_TTL
    FPG_TTL*AVISITN TRT01PN*FPG_TTL*AVISITN /DDFM =KR;
  REPEATED AVISITN/SUB=USUBJID TYPE=UN;
  LSMEANS TRT01PN*FPG_TTL*AVISITN/SLICE=AVISITN CL DIFF;
  ESTIMATE 'Treatment difference at Week 26 for 1st Baseline FPG
  Tertile'
    TRT01PN -1 1
    TRT01PN*AVISITN      0 0 0 0 1 0 0 0 0 -1
```

```
TRT01PN*FPG_TTL*AVISITN 0 0 0 0 1 0 0 0 0 0  
0 0 0 0 0 0 0 0 0 0 -1  
0 0 0 0 0 0 0 0 0 0 /CL ;  
RUN;
```

5. Example SAS code for analysis on exposure-adjusted event rate with Poisson regression model

```
ODS OUTPUT LSMeans= Lsmeans Diffs=Diffs;  
proc genmod data=INDATA;  
  class USUBJID TRT01AN MCRIT2ML HBGR1 AGEGR1 METFMN CTRYGR1;  
  model NUMEVT1=TRT01AN MCRIT2ML HBGR1 AGEGR1 METFMN CTRYGR1/  
d=poisson offset=PYOFFSET;  
  repeated SUBJECT=USUBJID /corrw covb type=exch;  
  LSMEANS TRT01AN/ EXP ILINK E CL DIFF;  
run;
```

